3.3.1 Number of Participants

We anticipate 10-50 records will be returned in the Epic report each day that will be screened for eligibility. We aim to recruit 100 participants who meet all inclusion and exclusion criteria for the trial, for a total of approximately 50 each in the intervention and control arms. Screening and enrollment will continue until the target sample size has been reached, with a goal of recruiting 5-10 patients per week.

Eligibility Criteria/Vulnerable Populations

In order to be eligible for inclusion in the study, an individual must meet all of the following criteria:

- adults (age ≥ 18 years);
- admitted at YNHH (YS and SRC) on medical units;
- identified as having chronic pain and prescribed opioids.
- Have opioid dependence (evidenced by ongoing opioid prescription, meeting DSM-5 criteria for OUD, or clinical history)

Any individual who meets any of the following criteria will be excluded from participation in this study:

- active cancer
- current pregnancy
- hospice care/comfort measures only
- admission to inpatient psychiatry
- completed or planned Addiction Medicine consult during hospitalization

4. Study Methods/Procedures

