3.4 Study Procedures

All patients will receive standard hospital care. Patients who are identified as eligible for the study via screening in Epic will be approached during hospitalization, undergo informed consent, and be enrolled in the study. Those who consent will be asked questionnaires

related to patient reported outcomes of pain, anxiety, depression and quality of life at baseline. Patients will then be randomized on a 1:1 ratio to either the enhanced opioid stewardship program arm or a control (i.e., usual care) arm. Patients who are randomized to the intervention arm will have their medical record reviewed by both a pharmacist and a physician trained in pain and addiction medicine. The pharmacist and physician will provide best practice guidance via an Epic note to the primary care teams to consider, versus continuation with their usual care plan. All guidance will be voluntary for clinical teams to follow. All participants will be tracked daily in Epic for discharge status, and when discharge within 48 hours is anticipated, the study team will perform the final patient interview, which will be very similar to the baseline interview and composed of questionnaires related to pain, anxiety, depression, and quality of life. Medical record abstraction will be performed to abstract relevant characteristics of each participant's hospitalization, use of guideline-based best practices for pain management and opioid stewardship at discharge, and incidence of readmissions and ED visits within 30 days after discharge for the hospitalization during which the participant was recruited.

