3.7.2 Sample Size Considerations

This pilot trial was not developed with power in mind to find a particular effect size in outcomes between study arms; hence we do not include power calculations.

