3.7.3 Planned Analyses

Due to the pilot nature of this trial, statistical considerations will consist primarily of bivariate analyses (i.e., t-tests, rank sum, and chi-square tests, as appropriate to variable type) to ensure balance of covariates between randomization groups and also to explore unadjusted associations between randomization groups and our outcomes. Exploratory regression analyses may be utilized to evaluate multivariable-adjusted associations between randomization groups and our outcomes, particularly if an imbalance between covariates among randomization groups is discovered.

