3.7.4 Analysis of Subject Characteristics (if applicable)

Subject characteristics will be evaluated using standard descriptive statistics and bivariate analyses (i.e., t-tests, rank sum, and chi-square test) to evaluate differences between intervention and control arms.

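### Significance tests of baseline characteristics cannot secure balance between randomised arms, and a chance imbalance found this way can steer the optional adjusted efficacy analyses (minor)

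*Combined protocol and SAP*

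**What the plan says.** The statistical text sits in sections 3.7.1, 3.7.3 and 3.7.4 of the combined protocol and SAP. Sections 3.7.1 and 3.7.3 carry the same statement: simple two-group tests will be used "to ensure balance of covariates between randomization groups and also to explore unadjusted associations between randomization groups and our outcomes". Section 3.7.4 repeats the baseline testing, planning "bivariate analyses (i.e., t-tests, rank sum, and chi-square test) to evaluate differences between intervention and control arms" alongside descriptive statistics.

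On adjustment, section 3.7.3 says: "Exploratory regression analyses may be utilized to evaluate multivariable-adjusted associations between randomization groups and our outcomes", and this "particularly if an imbalance between covariates among randomization groups is discovered". The plan names no covariates, does not define imbalance, sets no p-value cut-off, and does not say whether the adjusted or the unadjusted estimate leads.

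The setting is a pilot. The primary outcomes in section 3.2.1 are descriptive measures of recruitment and retention. Efficacy is a secondary matter (section 2.3). Section 3.7.2 adds: "This pilot trial was not developed with power in mind to find a particular effect size in outcomes between study arms".

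**The concern.** When allocation is properly random, any baseline difference between arms is a chance difference, so the null hypothesis of a baseline test is true by design. The test cannot bring balance about. A non-significant result does not show that the arms are alike, and a significant one does not show that the difference matters. What matters for adjustment is whether the covariate predicts the outcome, and a between-arm test carries no information on that.

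The only tool the plan offers for finding an imbalance is the significance test. Reading that test as the prompt for regression is therefore natural, even though the text does not say so outright. If it is used that way, covariates enter the model because of a chance result rather than for prognostic reasons, and a prognostic covariate that passes the test may be left out. At stake are the precision and interpretability of the preliminary-efficacy estimates, which section 4.15 intends for a manuscript and for future grant applications.

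**Working it through.** **Inputs from the documents.** Total size: "We aim to recruit 100 participants who meet all inclusion and exclusion criteria for the trial" (section 3.3.1), "for a total of approximately 50 each in the intervention and control arms". Allocation: "Patients will then be randomized on a 1:1 ratio" (section 3.4). The plan gives no alpha, SD, effect size or power, so there is no figure of its own to reproduce.

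**Assumptions.** Two-sided 0.05; normal covariate and outcome; covariate-outcome correlation 0.3, 0.5 or 0.7; d=0.5 as an illustration only.

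**1. What a non-significant baseline test allows.** The largest standardised difference that stays non-significant with 50 per arm is t(0.975, 98 df) × √(2/50) = 1.984 × 0.2 = 0.397, or about 0.40 SD.

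**2. How often a test fires by chance.** For k independent tests, the chance of at least one p<0.05 is 1 − 0.95^k: 23% for k=5, 40% for k=10, 64% for k=20. The number of baseline variables is an assumption. Positively correlated measures would give lower figures.

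**3. Operating characteristics if the trigger were baseline p<0.05.** Simulation with 50 per arm, 20,000 trials per scenario and one covariate:

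| Correlation | Size, adjust only if baseline p<0.05 | Power at d=0.5, always adjust | Size if the smaller of the unadjusted and adjusted p is reported |
|---|---|---|---|
| 0.3 | 5.1% | 73% | 6.5% |
| 0.5 | 4.2% | 81% | 7.2% |
| 0.7 | 3.5% | 93% | 8.1% |

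The simulation standard error for a size near 5% is √(0.05 × 0.95 / 20,000) = 0.15 percentage points, so 5.1% cannot be told apart from nominal. Adjusting only when triggered has 70%-72% power at all three correlations, hardly different from the 71% of the unadjusted t-test. Always adjusting keeps size at 4.7%-5.0%.

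With ten covariates jointly explaining 25% or 50% of outcome variance, size is 4.4% or 3.7% when only flagged covariates enter. It is 7.6% or 8.4% if the smaller of the unadjusted and fully adjusted p-values is reported. Choosing between the unadjusted result and the trigger-selected model gives only 5.0%-5.7% across the scenarios with one or ten covariates.

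**4. A near miss.** Suppose the baseline test gives z=1.9 (p=0.057) and the covariate is treated as balanced. Under no treatment effect the unadjusted outcome statistic then has mean ρ × 1.9 and SD √(1 − ρ²). For ρ=0.5 the mean is 0.95 and the SD 0.866, so the upper tail starts at (1.96 − 0.95)/0.866 = 1.17, and the false-positive risk is 12%. The same formula gives 7.7% for ρ=0.3 and 19% for ρ=0.7. These risks are conditional on one chosen event and are not the error rate of the procedure.

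**The case against.** The strongest reply is that the decision rule simulated above is not in the protocol. Regression is optional and exploratory, imbalance is only a particular reason for it, no threshold is given, and the unadjusted comparisons are planned in any case. Nothing says that an adjusted result would replace an unadjusted one. This stands. A reader might infer that chance p-values decide which efficacy result is emphasised, but the documents do not support that. They leave the choice open, and an observed imbalance can steer it.

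Second, no alpha and no confirmatory efficacy test are declared, so the plan states no error rate that could be breached. A reader might also infer that the approach inflates false positives. The figures point the other way: following the trigger is nominal to conservative overall, and modest inflation needs selective reporting. This stands too, although any p-value or interval that is reported will still be read at its nominal level.

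Third, the power gain comes from prespecified adjustment for a prognostic covariate, not from removing the baseline tests, and at a correlation of 0.3 it is only 70% against 73%. That is correct, and the two changes should not be credited with each other's benefit.

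Fourth, adjusting for an imbalanced prognostic covariate is a sound instinct. When a single covariate explaining 25% or 50% of outcome variance is flagged, the unadjusted test has conditional error of 19% or 34%, and adjustment brings it to 4.9% or 5.7%. This supports adjusting for prognostic covariates. It does not support using a significance test to find them.

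None of these replies rescues the stated purpose of the tests.

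**Conclusion.** The point holds in limited form. Baseline significance tests cannot secure balance after randomisation, and they do not identify prognostic covariates. Linking optional adjustment to a discovered imbalance, with no covariates, definition or lead estimate fixed, lets chance steer the adjusted analyses.

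Severity is minor. The primary feasibility outcomes are untouched; only the secondary preliminary-efficacy comparisons are affected. The non-significance limit of about 0.40 SD rests on the planned arm size and an assumed two-sided 0.05. The size and power figures rest further on an assumed p<0.05 trigger, assumed correlations and an illustrative d=0.5, none of which the documents give. The practical loss is mainly forgone precision: small at a correlation of 0.3 and substantial at 0.7.

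**What to change.** - In sections 3.7.1, 3.7.3 and 3.7.4, delete the between-arm tests of baseline characteristics. Present these by arm as means with SD, medians with interquartile range, or percentages; section 3.7.4 already plans descriptive statistics.
- In sections 3.7.1 and 3.7.3, replace the imbalance trigger with wording such as: *Any adjusted analysis will use a short set of covariates chosen on prognostic grounds before outcome data are seen, and will use them regardless of the imbalance observed.* For the pain and PHQ-4 outcomes the natural covariate is the baseline score, which section 3.6.3 already collects with the same questions as the final interview.
- State in advance, for each efficacy outcome, whether the adjusted or the unadjusted estimate leads. This closes the route to the 6.5%-8.1% inflation.

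The cost is wording in three subsections. No new data are needed, and trial conduct does not change.

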3.7.4 Analysis of Subject Characteristics (if applicable)

Subject characteristics will be evaluated using standard descriptive statistics and bivariate analyses (i.e., t-tests, rank sum, and chi-square test) to evaluate differences between intervention and control arms.

3.7.5 Interim Analysis (if applicable)

n/a

3.7.6 Handling of Missing Data

Approaches to manage missing data will not be implemented in this pilot study- missing data will indeed be part of our feasibility outcomes.

5 Trial Administration

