3.4.2 Adverse Events Definition and Reporting

Because the trial will not directly intervene on the clinical care of participants but will rather offer suggestions for care of participants with regard to pain management and opioid stewardship to a given participant's medical team, we anticipate that the risk for adverse events that are attributable to participation in the clinical trial will be minimal. We will monitor all participants during their participation in the trial for (1) death, (2) development of an adverse reaction to a recommended intervention (e.g., new medication) requiring medical care, and (3) increases in pain assessed via the numeric rating scale (standard hospital practice) requiring a change in medical care. We will notify the Yale HIC of these adverse events, and any other anticipated adverse events, immediately upon notification of the PI and will provide written documentation within 5 days.

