3.6.3 Study Visits (if applicable)

There will be up to 3 study visits with each participant, which will take place during hospitalization or in the first week after hospital discharge.

The first study visit will be for recruitment and enrollment. This visit will follow the format described in Section 3.6.2. This visit will last approximately 30 minutes.

The second study visit will be for completion of the baseline interview. This study visit may occur directly after enrollment. During this interview, participants will be asked questions related to pain, depression, and anxiety. Pain will be assessed using an abridged version of the Brief Pain Inventory,¹ which will take 5 minutes to complete. Depression and anxiety will be assessed with the Patient Health Questionnaire-4,² which will take 2 minutes to complete. They will also be asked demographic questions, for descriptive purposes. The baseline interview visit will last approximately 15 minutes.

The third study visit will be for completion of the final interview, which will take place within 48 hours of anticipated discharge. Participants will answer questions identical to those asked in the baseline interview on pain, depression, and anxiety. They will also be asked one question regarding their satisfaction with pain: "How pleased are you with your pain outcome during this hospital visit?", which will be answered on a Likert-type scale. The final interview will last approximately 15 minutes.

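### With no missing-data method, the pain, PHQ-4 and satisfaction contrasts rest on interview completers only and can be biased when missingness acts differently in the two arms

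*Combined protocol and SAP*

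**What the plan says.** Section 3.7.6 reads: "Approaches to manage missing data will not be implemented in this pilot study". It goes on to count missingness among the feasibility outcomes. This is a deliberate rule and not an omission.

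The analyses in 3.7.3 are t, rank-sum and chi-square tests, used in part "to explore unadjusted associations between randomization groups and our outcomes". Regression is optional, is tied mainly to covariate imbalance, and names no covariates.

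Sections 3.4 and 3.6.3 provide one post-baseline interview covering pain (modified Brief Pain Inventory), PHQ-4 and satisfaction. It is triggered when the team expects discharge in the next 48 hours. Section 3.6.3 also says of the study visits in general: "which will take place during hospitalization or in the first week after hospital discharge".

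Section 3.2.1 makes completion of this interview, by arm, one of the primary feasibility outcomes. Section 3.4.2 monitors deaths, but no section says how a death enters the interview outcomes. The count of guideline-based care elements and the 30-day ED visits and readmissions come from the medical record (3.2.2).

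**The concern.** Reporting how many interviews are missing is a sound feasibility outcome. It does not make a comparison among completers a fair comparison of the randomized arms. The interview depends on discharge being foreseen, so patients who leave unexpectedly, withdraw or die are the ones most likely to lack final scores. A link between missingness, arm and pain is plausible on the protocol's own account. Section 1.5.1 allows that best-practice pain management may temporarily increase pain or withdrawal discomfort, and only the intervention arm receives the added guidance.

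The contrasts will also be used. Section 2.1 states a directional hypothesis for pain at discharge, 2.3 describes both secondary objectives as concerning efficacy, and 4.15 plans a manuscript on these associations and use of the findings in grant applications. A biased estimate could carry forward into the design of a larger trial.

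**Working it through.** **Inputs from the documents.** The target is 100 patients, "for a total of approximately 50 each in the intervention and control arms" (3.3.1), with 1:1 allocation (3.4). On power, 3.7.2 says "hence we do not include power calculations", so the plan has no figure to reproduce. It gives no alpha, SD, expected non-completion or score gap.

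**Assumptions.** No true effect, a two-sided 5% test, a normal approximation, and scores in SD units. All missing proportions and gaps below are assumed.

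**Formula.** Let m be the missing proportion in an arm and δ the mean of missing patients minus the mean of observed patients. Then true arm mean = observed mean + m × δ. The bias of the observed contrast (intervention minus control) is

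bias = m_C × δ_C − m_I × δ_I.

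The standard error is √(1/n_I + 1/n_C), with n = 50 × (1 − m). The rejection rate is Φ(|bias|/SE − 1.96) + Φ(−|bias|/SE − 1.96).

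| m_I / m_C | δ_I / δ_C (SD) | Bias (SD) | SE | Rejection rate |
|---|---|---|---|---|
| 20% / 20% | 0.5 / 0.5 | 0.10 − 0.10 = 0 | 0.224 | 5.0% |
| 10% / 30% | 0.5 / 0.5 | 0.15 − 0.05 = 0.10 | 0.225 | 7.3% |
| 20% / 20% | 0.5 / 0 | 0 − 0.10 = −0.10 | 0.224 | 7.3% |
| 10% / 30% | 1 / 1 | 0.30 − 0.10 = 0.20 | 0.225 | 14.4% |
| 20% / 20% | 0.5 / −0.5 | −0.10 − 0.10 = −0.20 | 0.224 | 14.5% |
| 30% / 30% | 0.5 / −0.5 | −0.15 − 0.15 = −0.30 | 0.239 | 24.1% |

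The first row shows that missingness related to the score does no harm if it acts identically in both arms. Setting both gaps to zero gives zero bias at any pair of missing rates. Rows three, five and six show that equal completion rates do not guarantee an unbiased contrast.

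**On a 0–10 pain scale, with an assumed SD of 2.5 and the same gap in both arms**, the size of the bias is the gap times the difference in missing proportions:

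- 30% v 15% missing, 2-point gap (2/2.5 = 0.8 SD): bias 2 × 0.15 = 0.30 points; SE = 2.5 × √(1/35 + 1/42.5) = 0.57; 0.30/0.57 = 0.53 SE; rejection 8.2%.
- 30% v 10% missing, 3-point gap (3/2.5 = 1.2 SD): bias 3 × 0.20 = 0.60 points; SE = 2.5 × √(1/35 + 1/45) = 0.56; 0.60/0.56 is about 1.06 SE; rejection 18.7%.

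In SD units these biases are 0.12 and 0.24, inside the range of the table.

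**The case against.** The strongest reply is that this is a feasibility pilot. Its primary outcomes are recruitment and retention, the efficacy tests are called exploratory, no power is claimed, and the missing-data rule is disclosed. Completion will be reported by arm, so the amount of missingness will be visible. Baseline pain and PHQ-4 are collected, and adjusted regression is permitted. All of this stands, and it limits how serious the point is. It does not remove the point: a completion count says nothing about the gap δ, and the optional regression is not committed to the baseline score.

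Some stronger readings are tempting but unsupported:

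- A reader might infer that unequal completion, or missingness related to pain, is enough by itself to bias the contrast. The formula shows that neither is.
- A reader might infer that every unplanned discharge loses its interview. The first-week window in 3.6.3 may recover some, though it cannot help with deaths, refusals or lost contact.
- A reader might infer that the trial already holds everything a rich imputation model needs. Section 3.4.2 mentions numeric pain ratings only for adverse-event monitoring. Neither the last charted pain score nor discharge type is named among the abstracted items (3.4, 3.5, 4.6).

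The objection that imputation should not create scores for patients who died is also right. Death leaves the outcome undefined and needs its own rule.

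**Conclusion.** The point holds, at moderate weight. Under 3.7.6 and 3.7.3 the pain, PHQ-4 and satisfaction contrasts are unadjusted completer comparisons. They can be biased, and the plan includes no step to show how sensitive they are.

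Under the assumed inputs the bias runs from 0 to about 0.3 SD (0.30/0.239, about 1.3 standard errors), with rejection rates of 5% to about 24%. The 10% v 30% case with a 0.5 SD gap gives about 7%. A reader might take the upper figures as the expected error rate. The documents do not support that: those cases need opposite gaps in the two arms or gaps near a full SD, and no source for either is given. The plan also states no alpha, so these rates measure vulnerability and do not describe a breached guarantee.

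The point does not extend to the care-element count or to ED visits and readmissions, which do not depend on the interview.

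**What to change.** Keep missingness as a feasibility outcome. Replace the first clause of 3.7.6 with the following:

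1. Compare final pain and PHQ-4 between arms by regression adjusted for the baseline score, in all randomized patients with a final interview, analysed as randomized. This is still a completer analysis; it corrects only for missingness that the baseline score explains.
2. Report, by arm, the reasons for non-completion and the baseline pain and PHQ-4 of completers and non-completers.
3. Run one sensitivity analysis in survivors in which imputed final scores are shifted by an amount scaled to each instrument. A shift of k in one arm moves the contrast by m × k, so 20% missing and 0.5 SD moves it by 0.10 SD. Report deaths separately by arm and do not impute them.
4. Label the satisfaction contrast, which has no baseline value, as completer-only and descriptive.

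Reconcile the 48-hour timing of the final interview in 3.5 and 3.6.3 with the first-week-after-discharge window in 3.6.3. Flag any post-discharge interview by its timing, since 2.1 sets the outcome at hospital discharge. Use charted pain scores or discharge type in the imputation only if they are added to the abstraction form.

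The cost is modest extra analysis, some added model assumptions, and an amendment that needs IRB approval before use (4.2, 4.11). The sample size does not change.
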